Perceived Stress Scale	10		X	X	X	X	X
Social Support	3		X				
Religiosity	2	X					
Meditation Practice Log				X	X	X	X
Medical Utilization			X			X	X
Current Pharmacotherapy			X	X	X	X	X
Current Psychotherapy			X	X	X	X	X
Current other Mind-Body Tx			X	X	X	X	X
Demographics		X					
Psychiatric and Medical History			X				
Treatment Credibility/Expectancy	4			X			
Treatment Satisfaction	2					X	

Please attach copies, unless standard instruments are used

Research Related Delay to Treatment

Will research procedures result in a delay to treatment?

Yes

Maximum duration of delay to any treatment

There is a delay in receiving the mind-body therapy among those randomized to psychoeducation alone. However, the psychoeducation component is given to all participants and therefore there is no delay due to research procedures. We anticipate psychoeducation does confer some benefit as it includes valuable information about ways to reduce anxiety that are drawn from the CBT courses in the ThisWayUP courses from New South Wales University. In fact, this is why all groups will be receiving psychoeducation. Our

goal is to determine whether meditation and/or Kundalini Yoga confer additional benefit on top of that obtained from the psychoeducation. Our answer is that because all participants are receiving a therapeutic modality that should confer some benefit, we do not believe there is a delay in starting treatment.

Note on Psychoeducation: Psychoeducation appears to be an effective intervention for anxiety/depression and psychological distress according to two recent reviews (Donker, Griffiths, Cuijpers, & Christensen, 2009; Rodrigues et al., 2018). Donker et al. (2009) concluded that ‘brief passive psychoeducational interventions’ in particular may prove effective in reducing symptoms. Further, in a recent study conducted by Newby and colleagues (2018) examining online interventions for health anxiety, the authors found medium and significant reductions on health anxiety, generalized anxiety, depression and disability in the psychoeducation control group. A similar methodology to the current study was employed using 2-4-page fact sheets on anxiety-related topics delivered biweekly to study participants.

Maximum duration of delay to standard care or treatment of known efficacy

There is no delay as all participants will be receiving treatment.

All participants in this study will be able to continue during the study with whatever treatment they had been receiving prior to the start of this study. All participants are asked to not start new treatments during the first 8 weeks of the study. However, if medically or psychiatrically indicated, patients can start new treatments. We ask all patients to record any new treatments received. After the 8 weeks, participants can pursue other treatments as they wish; as a gift for completing our study, all participants will be offered a free subscription to Journey meditation recordings.

For follow-up purposes (3- and 6-months), we will collect information on any/all treatments (e.g., psychopharmacological, psychotherapeutic, mind-body therapies) that participants have engaged in during the post-treatment phase to control for this at the analysis stage.

There is no delay as a result of completing study questionnaires as these can be done on the same day as starting treatment.

Maximum duration of delay to standard care or treatment of known efficacy:
8 weeks

Treatment to be provided at the end of the study

All participants will be offered 8 weeks of Journey meditation at no cost to them.

Clinical Treatment Alternatives

Clinical treatment alternatives

Individuals do not have to participate in this study in order to obtain guidance in meditation or yoga

stretching. Both therapeutic modalities are available elsewhere. Individuals who wish to receive private treatment will be advised to consult with practitioners in their area.

Risks/Discomforts/Inconveniences

Risks that could be encountered during the study period

1. Quiet Meditation can sometimes lead to distress among individuals with a prior trauma history as they may re-visualize or remember the trauma during the quiet meditation.
2. The self-report questionnaires may lead to psychological distress among some individuals.
3. Stretching or postures may lead to discomfort.
4. Individuals are asked to not start new treatments during the course of this study. For patients who may wish to start an optional treatment, the 8 week delay in starting a new treatment may result in delay in receiving a potentially beneficial optional treatment.
5. Treatments in this study may not reduce symptoms of anxiety. There is also the potential risk that symptoms may worsen, because meditation and psychoeducation can increase awareness of body sensations, thoughts and feelings which people may find to be unpleasant.

Describe procedures for minimizing risks

1. Patients can stop the self-report questionnaires, postures, meditation or any aspect of the psychoeducation component of the study at any point or if distress is excessive
2. Participants whose PHQ8 scores on the 8 item scale indicate severe depression will be emailed and advised to seek mental health consultation. Participants who have a rating of "severe" on the PHQ8 for 2 consecutive assessments will be contacted by a study physician, advised to seek mental health consultation, and if deemed appropriate by the study clinician, withdrawn from the study.
3. Participants will be given a way to contact the study coordinator through ProofPilot. For emergencies, participants are advised in the consent form to go to their local emergency room or health care provider.
4. If discomfort arises during stretching or postures, patients will be told they can stop at any point
5. If a treatment is recommended by a physician as medically necessary, then that treatment is allowed - the participant merely needs to notify us of this change.

Methods to Protect Confidentiality

Describe methods to protect confidentiality

All data collected on the ProofPilot Platform in this online clinical trial is stored in an encrypted manner using Google's cloud hosting services. All of the participant medical information and research data will be kept confidential to the extent permitted by law. There are legal advocacy organizations that have the authority under State law to access otherwise confidential subject records, but they cannot re-disclose this information without a participant's consent. Any research data transmitted or stored electronically will use a number assigned to the participant, not the participant's name. Although the information provided by the participant may be shared in a deidentified manner with researchers who are not part of our University, their private identifying information (such as name, address, date of birth, or any other personal information that could be used to identify the participant) will not be released at any point.

Google is a cloud hosting company - meaning that data is not housed on one individual server, but spread across many - increasing physical security. ProofPilot is housed on multiple physical servers reducing the potential for a server outage to cause any issue with uptime or data loss. We also backup the material on a near real time basis and geolocate them in the case of a full out data loss in one location.

For more information, read the included Proofpilot White Paper on Security, Privacy, and Ethics.

In regards to patient/researcher communication, any emails sent from the study team to participants will be sent securely using '#encrypt' which was recommended by PsyIT.

Will the study be conducted under a certificate of confidentiality?

No

Direct Benefits to Subjects

Direct Benefits to Subjects

This study may or may not directly benefit participants.

However it is our hope that participation will allow us to evaluate two widely used meditation techniques to determine whether they help to reduce symptoms of illness anxiety. It is hoped that the knowledge gained in this study will be of benefit to patients suffering from illness anxiety related to COVID-19.

Compensation and/or Reimbursement

Will compensation or reimbursement for expenses be offered to subjects?

No

References

References

References

Basso et al. Brief, daily meditation enhances attention, memory, mood, and emotional regulation. *Behavioral Brain Research* 356 (2019); 208-220.

Blank et al. Effects of mindfulness exercises on anxiety and depression: systematic review and meta-analysis. *Behavior Research and Therapy*. 102 (2018) 25-35

Bults, M., et al., Perceptions and behavioral responses of the general public during the 2009 influenza A (H1N1) pandemic: a systematic review. *Disaster Med Public Health Prep*, 2015. 9(2): p. 207-19.

Collins C. Yoga: Intuition, preventive medicine, and treatment. *J Obstet Gynecol Neonatal Nurs*. 1998; 27:563-8

Gabriel et al. Kundalini Yoga for GAD *Int J Yoga Therapy* 28; 97-105

Grossman et al. MS quality of life, depression, and fatigue improve after mindfulness training. *Neurology*. 2010; 75(13):1141-1149

Hui Chew, Chiah Wei *Singapore Med Journ*. April 4, 2020 <https://doi.org/10.11622/smedj.2020046>

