Create or insert table to describe the inclusion criteria and methods to ascertain them

Inclusion Criteria	Ascertainment Method
1. Heightened Anxiety triggered or exacerbated by COVID-19	1. Self-report
2. Anxiety is at least mild- moderate in severity	2. GAD-7 score of 7 or greater
3. Age 18-70, male or female	3. Self-report
4. English speaking and living in the U.S.	4. Self-report
5. Consistent access to a smart phone, tablet or computer with internet.	5. Self-report

Create or insert table to describe the exclusion criteria and methods to ascertain them

Exclusion Criteria	Ascertainment Method
1. Current or past episode of psychosis or bipolar disorder	1. Self-report
2. Substance abuse within the last 6 months	2. Self-report
3. Pain disorder treated with opiate-based medication	3. Self-report
4. Current severe depression	4. Score of 20 or higher on PHQ8
5. Individuals with physical disability that might make study	5. Self-report

participation difficult

- | | |
|---|-----------------|
| 6. Unwillingness to complete questionnaires on-line, dedicate 30 minutes daily to meditation and/or stretching, or refrain from starting other new mind-body therapies during the study | 6. Self-report |
| 7. Individuals with a current daily practice of Kundalini yoga or meditation | 7. Self-report |
| 8. Individuals unwilling to be contacted for follow-up at 3-months and at 6-months | 8. Self-report |
| 9. Individuals unwilling to accept push notifications to their smart phone or computer | 9. Self-report |
| 10. Individuals with confirmed or suspected COVID-19 (including recovered cases) based on a positive test result, or CDC surveillance guidelines which require either: a) one of the following: cough, shortness of breath, or difficulty breathing; or b) two of the following: fever, chills, rigors, myalgia, headache, sore throat, new olfactory and taste disorder. (As per CDC guidelines, if an alternative explanation is more likely - based on patient history or medical evaluation - symptoms will not be considered suspicious for COVID-19). | 10. Self-report |
| 11. Individuals unwilling to provide the name and contact information of an individual in the case of emergency | 11. Self-report |
| 12. Pregnant women or women trying to become pregnant in the next 8 weeks. | 12. Self-report |
| 13. Individuals with an unstable medical illness over the last 12 months | 13. Self-report |

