| 14. Unwillingness to affirm sufficiently good medical health to safely participate in breathing exercises (e.g., 120 breaths per minute) and mild stretching exercises | 14. Self-report |
| 15. Lifetime history of suicide attempt, PTSD or psychiatric hospitalization | 15. Self-report |
| 16. Lifetime history of cardiac disease | 16. Self-report |
| 17. History over the last 12 months of lightheadedness, dizziness, vertigo, loss of balance | 17. Self-report |
| 18. Suicidal ideation with intent (i.e., suicide plan) in the past 6 months | 18. Self-report |

Waiver of Consent/Authorization

Indicate if you are requesting any of the following consent waivers

Waiver of consent for use of records that include protected health information (a HIPAA waiver of Authorization)

No

Waiver or alteration of consent

No

Waiver of documentation of consent

Yes

Waiver of parental consent

No

Consent Procedures

Is eligibility screening for this study conducted under a different IRB protocol?

No

Describe procedures used to obtain consent during the screening process

1. Patients will be asked to provide either a phone number or email address prior to entering the study portal on proofpilot. Patients will then be screened using our screening questions which will be provided on-line to prospective participants through the Proofpilot. Questions will include demographics, psychiatric, medical and symptom history, current meditation or yoga practices. No identifying information will be asked during this initial screening process.

2. Proofpilot will automatically determine whether the applicant meets criteria for inclusion and exclusion. Those who are eligible will then be directed to the next web page showing the study consent. Those who are not eligible will be advised to seek meditation and/or yoga in their community. If deemed eligible, patients will then enter a password to complete their account creation.

Describe Study Consent Procedures

After patients complete screening questions, they will be invited to read the consent form and then confirm decision to participate in the study as noted below.

Patients will be provided with an email address through which they can send any questions about the study to the study research coordinator ([name]) prior to completing the consent process (or after consent during the course of the study.) Our study staff will not be assessing eligibility; this will be based on the algorithm.

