If deemed eligible based on the answers related to I/E criteria, participants will be notified to complete informed consent on Proofpilot's website. Individuals who have questions about the study can email the study coordinator. Once consent is completed, they will then be asked to watch a video to encourage their full participation throughout the 8 weeks. They will then complete the baseline set of assessments prior to randomization.

If deemed ineligible to participate, participants will be encouraged to identify a yoga or meditation group in their community. If deemed ineligible due to suspected COVID-19 symptoms, patients will be advised to contact their local health care provider. Patients who score in the severe range for depression and who are excluded from participation will be advised to contact a local health provider for further evaluation of depression.

Study Procedure

Outcome Measures and other assessments. All participants will complete the baseline self-report questionnaires which assess current symptoms, impact of COVID-19, and additional medical and psychosocial history (including lifetime stressors). The full battery of Primary and Secondary outcome measure battery and COVID Follow-up queries will be conducted at baseline, and weeks 4, 8 (primary outcome), and at 3- and 6-months post-treatment. On a biweekly basis to week 8 (primary outcome time point), patients will complete the primary outcome measures and will be asked about their health status and any change in medication or treatment. In addition, on a daily basis, patients randomized to meditation or Kundalini Yoga will be asked to complete a daily log of their daily meditation/yoga practice.

1. Primary Outcome Measures

1. Symptom-based measures. GAD-7 (generalized anxiety); Whiteley-8 (health anxiety)

Secondary Outcome Measures

1. Symptom-based measures:

- PROMIS sleep disturbance
- PHQ8 (depression)
- SSS-8 (somatic symptoms)
- ERQ (emotion regulation)
- PSS-10 (stress)
- Brief hypervigilance scale

2. Health status: Overall Health in general (1 item)

3. Cognition: Neuro-QOL - Applied Cognition (8 items)

Moderators

Selected demographic variables

COVID-19 Exposure and related variables (“CRISIS” survey)

Intolerance of Uncertainty

Mental Health History

Prior Experience with Mind-body practices

Personal Religiosity or Spirituality (Importance; Identification)

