Primary aim#1	Aim 1: Test whether Kundalini Yoga with psychoeducation results in a significantly greater reduction in anxiety and multi-system symptom severity compared to psychoeducation alone.
Primary aim #2	Aim 2: Test whether a mindfulness meditation practice with psychoeducation leads to a significantly greater reduction in anxiety and multi-system symptom severity compared to psychoeducation alone.
Secondary aims and Exploratory goals:	
Aim 3: To assess whether treatment outcomes are moderated by COVID-19 related variables and personal variables.
 
Aim 4: To assess at the follow-up at month 3 whether patients have continued with the meditation practice and whether gains observed at week 8 have been sustained.
 
Aim 5: To assess whether there is a difference in both primary and secondary outcomes between the Kundalini Yoga and the meditation treatment groups.

Timing of Analysis	Analysis will be performed after the study is stopped for enrollment and a year after to make sure that all participants have finished their participation.
Analysis Population	We conduct analysis of a change score between baseline and week 8 for those who were randomized into one of the study arms and completed active treatment phase.
Missing Data	Missing data is treated as missing at random
Interim Analyses and Data Monitoring	There is no interim analysis for the protocol.
Primary aim#1 analysis	To investigate whether Kundalini Yoga with psychoeducation results in a significantly greater reduction in two primary outcome measures compared to psychoeducation alone, we will compare two groups of completers using one-sided t-test. P-value and estimation parameter value will be provided.
Primary aim#2 analysis	To investigate whether mindfulness meditation practice with psychoeducation leads to a significantly greater reduction in two primary outcome measures compared to psychoeducation alone, we will compare two groups of completers using one-sided t-test. P-value and estimation parameter value will be provided.

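### Existing yoga or meditation practice is possible in every arm and is asked about before randomisation, but the primary completer t-tests do not adjust for it

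*Combined protocol and SAP*

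**What the plan says.** **Eligibility.** In the Inclusion/Exclusion Criteria, criterion 7 excludes "Individuals with a current daily practice of Kundalini yoga or meditation". No criterion names less-than-daily practice, or other styles of yoga at any frequency. Criterion 6 requires only that participants "refrain from starting other new mind-body therapies during the study".

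**During the trial.** Under Research Related Delay to Treatment, participants are "able to continue during the study with whatever treatment they had been receiving prior to the start of this study". Nothing asks the psychoeducation-alone arm to stop an existing practice. The daily practice log is requested only from the two mind-body arms (Study Procedures).

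**Data collected.** The screening description in Consent Procedures states: "Questions will include demographics, psychiatric, medical and symptom history, current meditation or yoga practices". Study Procedures lists "Prior Experience with Mind-body practices" among the moderators. The assessment table has a row for other current mind-body treatment.

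**Analysis.** In the SAP, allocation is simple 1:1:1 with no strata. The analysis population is randomised participants who completed the active phase, and the outcome is change from baseline to week 8. For both primary aims the method is the same: "compared to psychoeducation alone, we will compare two groups of completers using one-sided t-test". No covariate is named. Aim 3 (moderators) is listed without a method. The Lay Summary and the delay-to-treatment section do promise to control for mind-body therapies in the analysis, but only for those used in the post-treatment follow-up.

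**The concern.** A participant assigned to psychoeducation alone may also be meditating several times a week, or doing a non-Kundalini style of yoga every day. Such practice could relate to how much anxiety changes over 8 weeks and to whether a person completes a programme of daily yoga or meditation. A variable related to both outcome and completion is the kind that an analysis restricted to completers leaves open.

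The SAP treats missing data as missing at random. A t-test in completers conditions on nothing except arm. It therefore relies on completion being unrelated to outcome within each arm, which is stronger than missingness at random given measured baseline variables. Practice status is one such variable and is asked about before randomisation, yet neither primary test uses it. The plan accepts the principle for follow-up and does not apply it at week 8, the primary endpoint.

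At stake are the balance and the interpretation of both primary contrasts.

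**Working it through.** **1. Is existing practice possible in every arm?** Criterion 7 is limited by frequency (daily) and by type (Kundalini yoga or meditation). Criterion 6 is limited to new therapies. Continuation of prior treatment is open to all arms. Together these permit a non-daily or other-style practice in any arm. One step is inference: the continuation sentence speaks of treatment, not of self-directed habits. Criterion 6 points the same way.

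**2. How many completers are there?** The documents give no completer counts by arm. Inputs: 256 randomised (SAP, Sample size) and week-8 drop-out of 71%, 72% and 84% (Overall Progress). Assumption: equal arms, 256/3 = 85.3.
- Psychoeducation: 85.3 × 0.29 = 24.7, about 25
- Meditation: 85.3 × 0.28 = 23.9, about 24
- Kundalini yoga: 85.3 × 0.16 = 13.7, about 14

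The plan asked for 270 completers, or 90 per arm if equal. That figure cannot be reproduced, because no alpha, power, effect size or SD is stated. It serves here only as a reference size.

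**3. How well is practice balanced, even if completion is unrelated to it?** Let q be the share with an existing practice (not reported; assumed 10% to 40%). The SD of the difference in shares is √[q(1−q)(1/n₁+1/n₂)]. At q = 0.20:
- 90 v 90: √[0.16 × 0.0222] = 0.060
- 25 v 24: √[0.16 × 0.0817] = 0.114
- 25 v 14: √[0.16 × 0.1114] = 0.134

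Probability of a gap of at least 15 percentage points in either direction (normal approximation, rough at these sizes):

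| q | 90 v 90 | 25 v 24 (meditation) | 25 v 14 (yoga) |
|---|---|---|---|
| 10% | 0.1% | 8.0% | 13.4% |
| 20% | 1.2% | 18.9% | 26.1% |
| 30% | 2.8% | 25.2% | 32.7% |
| 40% | 4.0% | 28.4% | 35.9% |

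Chance imbalance of this kind is noise that the t-test's standard error already allows for. It becomes bias only if completion depends on practice differently by arm. The documents give no data on that.

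**4. How far would such a gap move the result?** If practice shifted the change score by 0.3 to 0.5 SD (assumed), a 15-point gap would move the unadjusted difference by 0.15 × 0.3 = 0.045 to 0.15 × 0.5 = 0.075 SD, in a direction that cannot be stated. The standard errors, in SD units, are √(1/25+1/24) = 0.286 for meditation and √(1/25+1/14) = 0.334 for yoga. The shift is thus about 0.16 to 0.26 of a standard error for meditation and 0.13 to 0.22 for yoga. This is a sensitivity to an assumed gap, not an estimate of bias.

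**The case against.** The strongest reply is that this is an add-on trial with prior treatment openly continued in all arms. On that view, psychoeducation alone names the assigned study treatment, and randomisation balances prior practice in expectation. **This stands for all randomised participants.** A reader might infer that the control arm is contaminated and the primary contrast wrong. The documents do not support that: the contrast is valid for the population enrolled, and a practice-free population would be a different question. If existing practitioners gain less from the add-on, the average effect is smaller in that population, and a main-effect covariate would not restore it.

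A reader might also infer a spurious benefit for the active arms, on the reasoning that practitioners are likelier to finish them. That needs a prevalence, a completion ratio in each arm and an effect on change, none of which is documented. Practitioners might equally leave to follow their own routine. Higher drop-out in the yoga arm shows that retention differed, not who stayed. Because the outcome is change, a stable practice is partly reflected in the baseline score; it may still predict change.

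Nor do the meditation surveys cited under Description of Subject Population show that practice was common in this sample. They support only the expected gender and racial/ethnic mix.

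The plan does list prior experience as a moderator. **This stands in part**: the SAP gives no method for it, prior experience differs from current practice, and it plays no role in the primary tests.

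Finally, the completer restriction leaves every baseline variable exposed, not only this one. **That is correct**, and this point does not replace that larger issue.

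**Conclusion.** The point holds as a modest, inexpensive improvement to the analysis. It is not a design error. Eligibility permits existing practice in all arms, and practice is asked about before randomisation. The primary tests ignore it in completer groups of roughly 25, 24 and 14, where randomisation no longer protects its balance.

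The size and direction of any bias are unknown because prevalence is not reported. At an assumed 20%, a gap of 15 points or more has probability 18.9% (meditation) or 26.1% (yoga) by chance alone, and such a gap would move the result by well under one standard error. These figures rest on equal arms, the reported drop-out applied to 256 randomised, and the stated ranges for prevalence and effect on change.

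**What to change.** Enrolment is closed and only analysis remains, so the change is to the SAP and the report.

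1. Replace each primary t-test with a linear model of week-8 change containing arm, baseline score and current mind-body practice before randomisation (any versus none). First check that the screening answers allow this coding: the form is not shown and may record only what criterion 7 needs. If they do not, see whether the baseline item on other mind-body treatment can serve.
2. Report practice frequency by arm at randomisation and among week-8 completers. This replaces the assumptions above with facts.
3. Give an estimate in participants with no current practice, or a treatment-by-practice interaction, as supportive only, and specify it as part of the moderator analysis already listed.
4. Date the change and label it as made after enrolment closed.

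**Cost.** A regression replaces a t-test. Practice takes one degree of freedom and the baseline score another: on the counts above, residual degrees of freedom fall from 47 to 45 (meditation) and from 37 to 35 (yoga). The supportive estimate will be very imprecise.

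**Limits.** The covariate addresses imbalance. It does not undo dilution, and it does not cure the restriction to completers.

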 - c. Should the clinical assessment of depression after randomization indicate a rating in the severe range, an automatic email will be sent to the study coordinator and members of the team notifying them of the participant's high score. The study coordinator will then email the participant and recommend an evaluation by a local mental health provider. The patient will be asked to complete a follow-up depression rating 2 weeks later. If the score again falls in the severe range, one of our study clinicians will attempt to contact the patient by email or phone to recommend evaluation by a local mental health provider and to discuss withdrawal from the study. Withdrawal from the study will be determined according to the clinician's judgement after speaking with the participant, and assessing the costs/benefits to the participant of continuing with the intervention. This does not preclude the clinician from also making referrals or recommendations regarding additional treatment.
- You can upload charts or diagrams if any

Criteria for Early Discontinuation

Criteria for Early Discontinuation

Participants who develop severe depression during the course of this study that persists on the PHQ8 measure for 2 consecutive assessments will be discontinued from the study if appropriate based on clinical judgement. The patient will be contacted by one of the study physicians either by phone (or email). During this contact the physician will recommend referral to a local mental health provider. The study physician will speak with the participant at this time to determine whether it is in the best interests of the participant to remain in or be withdrawn from the study. Significant worsening of depression will be operationalized as a PHQ8 score (20 or higher) that falls in the severe range on 2 consecutive 1-week ratings.

Assessment Instruments

Create a table or give a brief description of the instruments that will be used for assessment

Measure	# of items	Screen	Baseline	Week 2	Week 4	Week 6	Week 8	3-month FU	6-month FU
COVID-19 exposure/status	2	X							
CRISIS Survey Baseline and Follow-up 3.0	10-30		X	X	X	X	X	X	X
GAD-7	7	X	X	X	X	X	X	X	X
Whiteley 8	8		X	X	X	X	X	X	X
SSS-8	8		X		X		X	X	X
PROMIS Sleep	4		X		X		X	X	X

Disturbance							
Emotion Regulation Questionnaire	10		X	X	X	X	X
Neuro-QOL - Applied Cognition	8		X	X	X	X	X
PHQ-8	8	X	X	X	X	X	X
Brief Hypervigilance Scale	5		X	X	X	X	X
Intolerance of Uncertainty Scale	12		X	X	X	X	X

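### The early-discontinuation rule gives conflicting intervals between the two severe PHQ-8 ratings, and its 1-week version does not match the PHQ-8 schedule

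*Combined protocol and SAP*

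**What the plan says.** The rule appears in four places in the protocol.

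- **Criteria for Early Discontinuation, general wording:** severe depression that "persists on the PHQ8 measure for 2 consecutive assessments will be discontinued from the study if appropriate based on clinical judgement". No interval is given.
- **Criteria for Early Discontinuation, operational wording:** "Significant worsening of depression will be operationalized as a PHQ8 score (20 or higher") when it "falls in the severe range on 2 consecutive 1-week ratings".
- **Study Procedures, contact with the research team, item c:** a severe score after randomisation sends an automatic email to the study team, and the coordinator recommends a local evaluation. Then: "The patient will be asked to complete a follow-up depression rating 2 weeks later". A second severe score leads to an attempt at clinician contact and a discussion of withdrawal.
- **Procedures for minimizing risks, item 2:** participants rated severe "on the PHQ8 for 2 consecutive assessments will be contacted by a study physician". Again no interval is given.

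On timing, Study Procedures lists the PHQ-8 among the secondary measures and says the full battery is "conducted at baseline, and weeks 4, 8 (primary outcome), and at 3- and 6-months post-treatment". Only the primary measures (GAD-7 and Whiteley-8), health status and treatment changes are collected every 2 weeks. The column heads in Assessment Instruments are screen, baseline, weeks 2, 4, 6 and 8, and the two follow-ups.

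The treatment descriptions and the SAP's Study Design entry also give 2-week questionnaire intervals. The Lay Summary and the Background say instead that assessment is weekly up to week 8, without naming an instrument.

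**The concern.** This is the only criterion listed under Criteria for Early Discontinuation, in a trial run online. Its operational definition relies on a rating frequency that the detailed schedule does not provide for the PHQ-8, and it disagrees with the repeat interval given just before it. Two members of staff following different sections could act on the same participant at different times.

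There is also a smaller consequence for the analysis. The SAP's Analysis Population is limited to randomised participants who finished the treatment phase, and both primary comparisons are t-tests among completers. A participant withdrawn under this rule before week 8 leaves the primary analysis because of a bad outcome. The SAP treats missing data as missing at random, but a two-group t-test on completers makes no use of the PHQ-8 scores that led to the withdrawal. So which version was applied can affect who is analysed.

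**Working it through.** This is a consistency check of intervals; no power or error-rate calculation is involved.

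**Inputs.** The threshold is a PHQ-8 of 20 or more. The stated spacing is 1 week (Criteria for Early Discontinuation) or 2 weeks (item c). Week 0 is baseline. The follow-ups are 3 and 6 months after week 8: 3 × 52/12 = 13 weeks, so about weeks 21 and 34.

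**Assumption.** Both severe ratings fall after randomisation, as item c specifies. The screening rating cannot be one of the pair for an enrolled participant, because a PHQ-8 of 20 or more at screening is an exclusion.

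**Trying to reproduce the stated 1-week spacing.** For each schedule the text could support, I took the gaps between successive ratings and the week at which a second consecutive post-randomisation rating first exists.

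| Source | PHQ-8 ratings (week) | Gaps (weeks) | Pairs 1 week apart | Earliest second rating |
|---|---|---|---|---|
| Study Procedures, full battery | 0, 4, 8, 21, 34 | 4, 4, 13, 13 | 0 | week 8 |
| Same, plus item c repeat | 4, then 4 + 2 = 6 | 2 | 0 | week 6 |
| Assessment table, most generous reading | 0, 2, 4, 6, 8, 21, 34 | 2, 2, 2, 2, 13, 13 | 0 | week 4 |
| Lay Summary and Background, general sentence | 0 to 8 weekly, 21, 34 | eight of 1, then 13, 13 | 8 | week 2 |

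The 1-week spacing is reproduced only from the general sentence. Neither the Study Procedures schedule nor any reading of the assessment table gives it, since the table has no odd-week column. On the Study Procedures schedule, three intervals have to be reconciled: 1 week (definition), 2 weeks (triggered repeat) and 4 weeks (scheduled gap during treatment).

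**How far the table can be used.** The PHQ-8 row lost its column positions when the text was extracted, so I do not treat it as an error. Its six marks would fit screening plus the five visits shown in the intact SSS-8 row (baseline, weeks 4 and 8, both follow-ups), which agrees with Study Procedures. Read strictly from left to right, they would fall on screen, baseline and weeks 2, 4, 6 and 8. Neither placement yields a 1-week pair.

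**Link to the analysis population.** If the second severe rating is the week 8 assessment, the participant already has an endpoint rating and nothing is lost. If it comes at week 6 and the clinician then withdraws the participant, the week 8 value may be missing and the participant is not a completer.

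For scale, the Annual Progress section reports week 8 drop-out of 71% (psychoeducation alone), 72% (meditation) and 84% (Kundalini Yoga). Arm sizes are not given. Assuming an equal split, 256/3 = 85.3 per arm, so those remaining are about 85.3 × 0.29 = 25, 85.3 × 0.28 = 24 and 85.3 × 0.16 = 14. In groups that small, a few removals driven by outcome could matter. Whether any occurred is not stated.

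**The case against.** The strongest reply is that item c works without a scheduled second rating. The first severe score triggers an alert, a requested repeat 2 weeks later and an attempt at clinician contact, with withdrawal decided by judgement. The wording about two consecutive assessments is compatible with that repeat. This stands. A reader might infer that the safety rule cannot be run at all, or that it could stop nobody during treatment. The documents support neither: only the 1-week definition fails, and item c can act by week 6. Nor are participants without staff contact, since item c provides for it.

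A second reply is that weekly assessment is mentioned, in the Lay Summary and the Background. That is correct, so it would be too strong to say that weekly ratings appear nowhere. But the sentence names no instrument and conflicts with Study Procedures, the treatment descriptions, the assessment table and the SAP's Study Design entry. It adds to what must be reconciled and does not establish a weekly PHQ-8.

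A third reply is that the phrase about 1-week ratings might describe the period each rating covers, not the spacing. The documents do not say so. If that was meant, the definition would state no interval, which would still need correcting.

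Finally, a reader might infer that the primary result is biased by this rule. That is not shown. Meeting the rule does not mean removal, only withdrawals before week 8 could matter, and no count is available. The restriction to completers is a broader issue, of which this is one route. It is also true that rewording can no longer protect participants, since none remain enrolled.

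**Conclusion.** The point holds as an internal contradiction in a stated safety threshold. The 1-week definition conflicts with the 2-week repeat and cannot be met from the PHQ-8 ratings scheduled in Study Procedures. Following item c after a severe week 4 score, the rule could first be met at week 6; using consecutive scheduled ratings, at week 8, the end of treatment. It could be earlier if the PHQ-8 was in fact collected more often: week 4 on a 2-week schedule, week 2 on a weekly one.

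This rests on three assumptions: that the 1-week wording refers to spacing, that both ratings fall after randomisation, and that the PHQ-8 followed the schedule for secondary measures. The consequence for the analysis is limited to participants withdrawn at clinical discretion before week 8, whose number is unknown. It should be corrected and reported, but it does not by itself show that the safety procedure failed or that the result is biased.

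**What to change.** Reconcile the Lay Summary, Background, Study Procedures (outcome measures and item c), Criteria for Early Discontinuation, Assessment Instruments and Procedures for minimizing risks, so that the rule names one interval matching a PHQ-8 rating the trial collects. Which interval is right is for the sponsor to decide.

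Because only data analysis is ongoing, the part that still has effect is in the SAP and the report:

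- State which version of the rule was applied and when the PHQ-8 was actually collected.
- Report by arm how many participants met the rule and how many were withdrawn under it, with the week of withdrawal.
- Keep anyone withdrawn before week 8 in an as-randomised analysis, using the ratings they gave up to withdrawal.

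The cost is some rewording, one table by arm and a little more analysis. PHQ-8 data alone will not identify withdrawals, so withdrawal records must be checked. The exit assessment and reason questionnaire described under Study Drop-outs may help, but the documents do not describe a log of clinician-decided withdrawals.
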